## BACKGROUND

Identification of the epidural space involves recognition of a change in pressure from one tissue plane to another. This drop of pressure, called “loss of resistance” (LOR), across a band of connective tissue into the epidural space is detected using a needle-syringe apparatus. The operator applies pressure to the plunger of the syringe until the drop in pressure is identified when the plunger collapses. The epidural catheter, a small tube that is inserted into the epidural space to give the medication, is then advanced using the needle as a guide. Confidence in locating the epidural space is based on clarity of the loss of resistance and the ease of threading the epidural catheter.

When there is difficulty in advancing the epidural catheter after the epidural space has been identified, several maneuvers are performed in order to correct the problem. These include: injecting saline through the needle to “expand” the epidural space, advancing the needle tip 1-2 mm, inserting a new flexible epidural catheter, inserting a new non-flexible epidural catheter, rotating the needle bevel, changing a patient’s posture, pulling the needle back to re-engage the *ligamentum flavum* and then performing a second LOR technique, and removing the needle entirely and performing a new placement at the same or different interspace (1). Each time a new maneuver is performed, this is considered a new attempt at threading the epidural catheter into the epidural space. Not succeeding on threading the epidural catheter correctly into the epidural space on the very first try is considered a “failure to thread,” however these maneuvers are performed until adequate labor analgesia is established in all patients. Establishing labor analgesia on the first epidural catheter threading attempt reduces the amount of time between when the epidural is requested and when pain relief is administered. A “more successful”

epidural threading attempt is related to a decrease in the time required to thread the epidural and adequately relieve labor pain.

Difficulty to thread an epidural catheter is distinct from a far more serious complication, epidural failure (2). Epidural failure is when the epidural fails to provide adequate pain management. Per internal data review, there is no statistically significant difference between epidural failure rates in literature (2) and the epidural failure rate on the Labor and Delivery floor (9th floor) of the University of Michigan von Voitlander Women's Hospital.

Two different epidural catheter kits, Arrow FlexTip Plus® Epidural Catheterization Kit (Arrow® International, Cleveland, OH) and Perifix® FX Springwound Epidural Catheter Kit (B.Braun Medical Inc., Bethlem, PA) are currently in use on the Labor and Delivery floor (9th floor) of the University of Michigan von Voitlander Women's Hospital. Both kits are standard of care and are routinely used to place epidurals at von Voitlander.

## **OBJECTIVES**

The aim of the study is to assess if there is a difference in ability to thread the epidural catheter (measured in time to thread) from two different pain management kits: Arrow® and B.Braun®. In order to improve patient care at U of M, if there is a difference in the time to thread epidurals with one kit over the other (i.e. one epidural catheter threads more easily than the other), we would like to use the kit with decreased time to thread in the future. We would like to make this comparison based on data.

Our hypothesis is that there is no difference in the average time required for clinicians to thread the epidural catheters from the Arrow® and B.Braun® pain management kits.

The primary outcome is to compare the number of epidural threading attempts between the Arrow® and B.Braun® pain management kits.

Secondary objectives of this study are to compare the difference in average time required to advance the epidural catheter, the number of epidural needle manipulations once the epidural space has been established, the incidence of unintended dural punctures, the incidence of paresthesia, and the incidence of epidural intravascular cannulations between the two different kit vendors.

Our findings may not be generalizable to other facilities due to local practices (presence or absence of trainees, training level of the residents, obesity of patients, etc.) but data will be made publically available. This project is primarily intended to improve patient care at U of M via scientific level analysis.

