Once, the epidural catheter has been threaded successfully, the clinician will apply negative pressure to the catheter through a syringe in order to rule out blood or cerebro-spinal fluid (CSF) aspiration. If aspiration of blood and CSF is negative, the patient will be given our standard medications consisting of 2 ml Lidocaine 1.5% with epinephrine 1:200,000 to rule out intrathecal catheter placement. Following 2 minutes, the patients will be given additional 3 ml from the lidocaine and epinephrine mixture in order to rule out intravascular cannulation. In addition, a standard loading bolus of bupivacaine 0.125% with fentanyl 3 mcg/ml will be administered in three fractionated doses of 5 ml each, through an epidural pump. All patients will be then connected to a programmed intermittent epidural bolus pump with the following settings: bupivacaine 0.125% with fentanyl 3 mcg/ml, programmed intermittent bolus 6 ml every 45 minutes. Patient's demand bolus 6 ml every 15 minutes, without baseline infusion.

If the epidural catheter cannot be sufficiently advanced into the epidural space, one or more of the following maneuvers will be adopted: additional saline will be administered through the Tuohy needle; alternatively, a new flexible epidural catheter can be inserted; if the catheter advances following one of these afore-mentioned maneuvers, the thread will be considered successful with minor adjustments. Conversely, if the needle is rotated, re-angled, redrawn and

re-advanced or advanced blindly, these will all be considered as major needle manipulations and recorded as failure of that attempt to advance the epidural catheter. Further attempts are made until proper epidural analgesia is established.

Establishment of successful labor analgesia will be defined at a verbal analogue score equal to or less than 10 on a 100-point scale within 30 min from the standard epidural medication administration. All data related to the technical aspects of the epidural placement will be collected in the form shown in the appendix. The goal of both study groups is the management of labor pain.

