### *Study Size*

In order to determine the study size, we looked at 114 consecutive epidural placements as part of our routine quality assurance with the Arrow® Epidural Catheterization Kit at Von Voigtlander. We found that in 11% (n=12) of epidurals placed, the epidural catheter did not thread on the first attempt. In a separate quality assurance check we retrospectively reviewed 100 epidural placements finding out that in 1% (n=1) of epidurals placed, the epidural catheter did not thread on the first attempt. A sample-size analysis for the primary outcome shows that 107 epidural placements per group would provide a power of 80% to detect a difference in proportion between the two techniques of 0.10 at the 0.05 level. Considering an attrition of 10-20% for follow-up and data missing, a total number of 240 epidural placements will be collected. Power calculations were computed using PASS 14.

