### *Statistical Analysis*

Statistical analysis will be performed using SAS 9.3 (SAS Institute, Cary, NC). The

primary outcome will be the success rate of epidural catheter threaded with each epidural kit, which will be compared by group using a chi-square test or Fisher's exact test, as appropriate. The secondary outcomes will be analyzed as follows: the difference in number of epidural attempts will be compared using the Mann-Whitney test; the difference in time to perform the epidural start to finish defined as the time the epidural needle is inserted through the patient's skin to the end of the catheter thread will be compared using the Student's t-test; the difference in the incidence of epidural needle manipulations once the epidural space has been established will be compared using the Chi-Square or Fisher's exact test, as appropriate; the difference in incidence of unintended dural puncture, paresthesia, and intravascular cannulations will be compared using the chi-square or Fisher's exact test, as appropriate. In addition, the difference in unsatisfactory labor analgesia with Arrow® and B.Braun® kits will be compared through the chi-square or Fisher's exact test, as appropriate, by looking at the difference in percentages of patients who have a verbal analogue pain score equal or less than 10 (scale 0 to 100) at 30 minutes following epidural medication administration. A p-value of 0.05 throughout will be considered statistically significant.

All statistical analyses will be performed using SAS 9.3 (SAS Institute, Cary, NC).

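### The plan declares two different primary outcomes, and the one that matches the sample size has no single rule for scoring a successful thread

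*Combined protocol and SAP*

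**What the plan says.** **Primary outcome.** The Objectives say "The primary outcome is to compare the number of epidural threading attempts between the" two kits. The Statistical Analysis section says the "primary outcome will be the success rate of epidural catheter threaded with each epidural kit", tested by chi-square or Fisher's exact test. Among the secondary outcomes it then lists: "the difference in number of epidural attempts will be compared using the Mann-Whitney test".

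**Sample size.** Study Size takes a proportion from two quality-assurance reviews. In the Arrow review, "in 11% (n=12) of epidurals placed, the epidural catheter did not thread on the first attempt". In the other review the figure was 1% (1 of 100). From these, "107 epidural placements per group would provide a power of 80% to detect a difference in proportion" of 0.10, and 240 placements in total are planned.

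**Success and failure.** The Background says "Not succeeding on threading the epidural catheter correctly into the epidural space on the very first try is considered a" failure to thread. It also says "Each time a new maneuver is performed, this is considered a new attempt at threading the epidural catheter into the epidural space", after a list of maneuvers that includes saline injection and a new catheter. The section on Equipment, Technique and Study Data Collection says that if the catheter advances after saline or a new flexible catheter, "the thread will be considered successful with minor adjustments". It records rotating, re-angling, re-advancing or blindly advancing the needle as failure of that attempt.

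**Counting attempts.** The same Equipment section counts an epidural attempt for each skin wheal, and another when the needle is withdrawn and re-advanced to regain loss of resistance. The study form marks only the repeat loss of resistance as an additional attempt. It also has a field for the number of additional attempts after loss of resistance, without a definition.

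**The concern.** A count compared by Mann-Whitney and a proportion compared by chi-square or Fisher are different outcomes with different tests, and each is called primary in one section. Naming the proportion as primary does not finish the job, because the Statistical Analysis section does not say what success is, and the sections that could supply a definition disagree.

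Two things are at stake. First, the study is open label and the form records most maneuvers separately, so the main scoring rules can all be derived from the same data. Unless the rule is fixed beforehand, it could be chosen after the results by kit are known. Second, the stated power belongs to whichever rule produced the 11% and 1%. If the analysis uses another rule, that power does not describe the primary analysis.

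**Working it through.** **1. The plan's own figure.** Inputs from Study Size: p1 = 0.11, p2 = 0.01, level 0.05 (taken as two-sided), power 80%. With d = 0.10 and mean rate 0.06:

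n0 = [1.960·√(2·0.06·0.94) + 0.842·√(0.11·0.89 + 0.01·0.99)]² / 0.10² = 87.3

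With continuity correction: n = (n0/4)·[1 + √(1 + 4/(n0·d))]² = 106.4, so 107 per group.

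This matches the plan. The arithmetic is sound, and it is the arithmetic of a binary outcome, as in Statistical Analysis, not of the count in the Objectives.

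**2. The scoring rules side by side.**

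| What happened before the catheter threaded | Background: first-try rule | Equipment section: success or failure | Equipment section: count of attempts |
|---|---|---|---|
| No maneuver | success | success | first attempt |
| Saline, or new flexible catheter | failure | success, minor adjustment | still first attempt |
| Needle rotated, re-angled or blindly advanced | failure | failure | still first attempt |
| Needle withdrawn, repeat loss of resistance | failure | failure | additional attempt |
| New skin wheal (new placement) | failure | not named separately | additional attempt |
| Posture change, or non-flexible catheter | failure | not classified | not counted |

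The words *first attempt* in Study Size do not select a column. Under the Background, saline starts a new attempt. Under the Equipment section's count it does not, and neither does rotating the needle.

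**3. Effect on power if the rules differ.** Suppose the 11% and 1% were counted by the Background rule and the analysis uses the Equipment section's success rule. Let s be the share of first-try failures that thread after saline or a new catheter. The documents do not give s, so 25%, 50% and 75% are assumed, equal in both kits. The rates become 0.11(1 − s) and 0.01(1 − s).

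Power is by full binomial enumeration with the planned test, using Fisher where an expected count is below 5 and chi-square otherwise. The 96 per group is 120 less the plan's upper attrition of 20% (120 × 0.8).

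| s | Rates | Power, 120 per group | Power, 107 | Power, 96 | n per group for 80%, planned test | n per group, plan's continuity-corrected formula |
|---|---|---|---|---|---|---|
| 0 | 11% vs 1% | 94% | 90% | 85% | – | 107 |
| 25% | 8.25% vs 0.75% | 81% | 73% | 64% | about 119 | 145 |
| 50% | 5.5% vs 0.5% | 49% | 40% | 32% | about 180 | 220 |
| 75% | 2.75% vs 0.25% | 9% | 6% | 4% | about 365 | 447 |

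The last two columns differ because the continuity-corrected formula is conservative relative to the planned test.

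**4. Unequal rescue.** At 120 per group with 50% rescue in the 11% group, power is 38% if the other group has no rescue (5.5% vs 1%) and 65% if all its failures are rescued (5.5% vs 0%).

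**5. Reverse case.** If the reviews used the Equipment section's rule and the analysis uses the Background's, the rates are divided by 1 − s: 14.7% vs 1.3%, 22% vs 2%, 44% vs 4%. Power at 107 per group is then 98% or more.

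All figures treat placements as independent, although kits are randomized by week. The attempt-count column is not modelled, because the documents give nothing on how often the needle is rotated, re-angled or blindly advanced.

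**The case against.** **The conflict over the primary is one sentence.** Study Size and Statistical Analysis agree on a proportion, and Study Size says its calculation is for the primary outcome. This stands: neither the sizing nor the primary test needs to change for that reason, and the repair is to the Objectives.

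**The Methods can be read as the operative rule.** The Background list carries a literature citation and is in the present tense, while the Equipment section is prospective and sets up a grade of success with minor adjustments. This is a fair reading, but it does not settle the matter. The Background text is worded as a definition and is the only place that defines a threading attempt, the term used in the Objectives. The Equipment section scores failure of an attempt, not of a placement, and its own count of attempts leaves a rotated needle within the first attempt while its failure rule scores it as a failure.

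**A reader might infer that the trial is underpowered.** The documents do not support that. No passage shows that the reviews and the analysis use different rules, and none gives the rescue share. At 25% rescue the planned 120 per group still reaches 80% if there is no attrition.

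**A reader might infer an inflated false-positive rate, or an interim efficacy look at about 120 placements.** Neither is shown. The harm from choosing a rule late cannot be sized from these documents. The midpoint review appears under data and safety monitoring and is not described as an efficacy test.

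**Conclusion.** The point holds. The plan as written fixes neither a single primary outcome nor a single way to score it. The disagreement between Objectives and Statistical Analysis is plain on the current text, and the sample size shows which of the two was intended. The missing definition of success is the more consequential half, because three readings of a first-attempt thread are available and most of what separates them is recorded on the form.

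The effect on power is conditional. If one rule is used throughout, 107 per group stands. If the 11% and 1% follow the Background rule and the analysis follows the Equipment section's, power at 120 per group falls from 94% to between 81% and 9% over an assumed rescue share of 25% to 75%, equal in both kits. In the reverse case it rises. These figures show why the rule must be stated. They are not an estimate of this trial's power.

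**What to change.** - In Objectives and Statistical Analysis, name one primary outcome: the proportion of placements in which the catheter does not thread on the first attempt, tested by chi-square or Fisher's exact test. Make the number of attempts secondary in both.
- Before data collection, state one scoring rule that classifies every listed maneuver: saline, new catheter, rotation, re-angling, blind advance, withdrawal with repeat loss of resistance, change of space, posture change and non-flexible catheter. Use the rule that produced the 11% and 1%.
- Reconcile the outcome wording of the Background, the Equipment section and the study form to that rule. This concerns scoring only, not how the placement is carried out.
- If the chosen rule differs from the one behind the 11% and 1%, restate the power.
- Define *threading attempt* and *epidural attempt* once each, and use them consistently.
- Report threads after minor adjustments separately.

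**Cost.** Protocol wording and a check of how the two quality-assurance reviews were counted. The form already has a box for a thread without maneuvers and lines for most of the others. It has none for posture change or a non-flexible catheter, and the Equipment section classifies neither, so lines are needed if those maneuvers are to be scored, including for the binary primary.

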## **METHODS**

### *Type of Study*

Comparative effectiveness study via an open label alternate treatment design with randomized scheduling.

### *Inclusion Criteria*

The Arrow® and B.Braun® epidural kits available in labor and delivery.

All patients requesting or requiring epidurals on the 9th floor (Labor and Delivery) of the University of Michigan von Voiglander Women's Hospital.

### *Exclusion Criteria*

Epidural kit not available at the moment of the study.

### *Randomization Procedure*

Epidural kits are available for eligible patients on labor and delivery Von Voiglander 9th floor who are requesting labor analgesia. Approximately 30 epidural placements occur in the obstetric service during any given week. These epidural placements are consistently performed by residents, faculty, and fellows in a sharable and equitable number. No group of individuals are specifically targeted.

A prospective alternating intervention study design with randomized weekly scheduling will allow for equal use of the two epidural kits. In weeks randomized to Arrow®, only Arrow®

kits will be available. In weeks randomized to B.Braun®, only B.Braun® epidural kits will be available. In order to target a sample size of 240 epidural placements (n=120/group), and assuming that every week 30 epidurals will be performed, in 8 weeks we should be able to finish the study. However, if at the end of the 8 weeks we have not reached the target sample size per kit group, we will continue to randomize kit use in the following weeks in order to achieve sufficient sample size. The randomization of the kit to be exclusively used each week will be generated through a password-secure computer ([www.randomization.com](http://www.randomization.com)) by the research assistant. The two available kits are:

1) FlexTip Plus® Epidural Catheterization Kit (Arrow® International, Cleveland, OH).

**OR**

2) Multi-orifice epidural kit: Perifix® FX Springwound Epidural Catheter Kit (B.Braun Medical Inc., Bethlem, PA).

However, the alternate pain management kit will remain accessible during the study if it is deemed necessary for a particular patient.

This study design is in consideration of the fact that retrospective analyses of large databases or patient records are subject to unknown biases, thus causation is difficult to assign.

(3) (4)

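### Kits are randomised by calendar week, but the sample size and every planned test treat placements as independent, so neither the 5% error rate nor the 80% power is assured if results vary by week

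*Combined protocol and SAP*

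**What the plan says.** The section Randomization Procedure makes the calendar week the unit of allocation: "The randomization of the kit to be exclusively used each week will be generated through a password-secure computer". On timing it says: "assuming that every week 30 epidurals will be performed, in 8 weeks we should be able to finish the study". The target is 240 placements, 120 per kit, so equal use means about four weeks per kit. If the target is missed, further weeks are randomised, but only to reach the placement count. The same section describes placements as "consistently performed by residents, faculty, and fellows in a sharable and equitable number" and notes that "the alternate pain management kit will remain accessible during the study if it is deemed necessary for a particular patient".

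Study Size states that "107 epidural placements per group would provide a power of 80% to detect a difference in proportion between the two techniques of 0.10", based on quality-assurance failure rates of 11% and 1%. The only inflation is for missing data: "Considering an attrition of 10-20% for follow-up and data missing, a total number of 240 epidural placements will be collected".

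Under Statistical Analysis the primary outcome is the threading success rate, "which will be compared by group using a chi-square test" or Fisher's exact test. Number of attempts gets a Mann-Whitney test and time a Student's t-test. Needle manipulations, complications and 30-minute analgesia get chi-square or Fisher tests. All are at placement level.

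No section gives an ICC, a design effect, a term for week or a week-level analysis. Training level and body mass index are recorded, and Table 1 splits failure by training level, but no planned kit comparison adjusts for either or for week.

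**The concern.** Placements in the same week share a staffing rota, a mix of trainees and a workload. If these move the failure rate from week to week, two placements in one week are more alike than two in different weeks. The whole of that shared component falls on one kit. A test that counts 240 independent placements then understates the variance of the kit difference, which in truth comes from about eight randomised units.

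Two things are at stake. First, Objectives says the hospital would adopt the better-performing kit. A chance difference between one set of four weeks and another could drive that choice. Second, the stated 80% power belongs to a test whose error rate is not assured. A test that respects the weeks has 8 - 2 = 6 degrees of freedom, and Study Size says nothing about its power. The placement-level secondary tests are exposed in the same way.

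**Working it through.** **1. Reproduce the plan's figure.** Inputs from Study Size: p1 = 0.11, p2 = 0.01, difference 0.10, alpha 0.05 (taken as two-sided), power 80%.

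- Uncorrected: n = [1.960 × √(2 × 0.06 × 0.94) + 0.842 × √(0.11 × 0.89 + 0.01 × 0.99)]² / 0.10² = (0.658 + 0.276)² / 0.01 ≈ 87.3.
- Continuity-corrected: (87.3 / 4) × [1 + √(1 + 4 / (87.3 × 0.10))]² ≈ 106.4, rounded up to 107.

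The stated 107 is therefore the two-sided, continuity-corrected formula for independent observations. It contains no design effect. For attrition, 107 / 0.9 = 118.9 and 107 / 0.8 = 133.8, so 120 per group covers the 10% end and leaves nothing for clustering.

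**2. Effective size.** With four weeks per kit and m analysed per week, effective size per kit = 4m / (1 + (m - 1) × ICC). The ICC range is an assumption.

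| ICC | 0 | 0.005 | 0.01 | 0.02 | 0.05 |
|---|---|---|---|---|---|
| 10% attrition (m = 27) | 108 | 96 | 86 | 71 | 47 |
| 20% attrition (m = 24) | 96 | 86 | 78 | 66 | 45 |

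With all 240 analysed, the effective size drops below 107 once ICC exceeds (120/107 - 1) / 29 = 0.004. Against the uncorrected 87.3 the threshold is (120/87.3 - 1) / 29 = 0.013. It is 0.009 after 10% attrition and 0.004 after 20%. None of these thresholds allows for lost degrees of freedom.

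**3. Type I error of the planned primary test.** Beta-binomial simulation, 4 + 4 weeks of 30, equal rates for both kits, 100,000 trials per setting. Chi-square is used if expected counts are at least 5, otherwise Fisher. Placements are analysed under the week's kit.

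| Failure rate | ICC 0 | 0.005 | 0.01 | 0.02 | 0.05 |
|---|---|---|---|---|---|
| 11% | 5.1% | 6.7% | 8.6% | 12.0% | 21.4% |
| 6% | 5.0% | 6.6% | 8.2% | 11.4% | 19.5% |
| 3% | 1.9% | 2.8% | 3.9% | 6.0% | 12.2% |
| 2% | 0.8% | 1.3% | 1.9% | 3.4% | 8.1% |

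After 10% / 20% attrition at a 6% rate the error is 7.2 / 6.2% at ICC 0.01 and 9.9 / 8.5% at 0.02. Scale: the SD of the weekly rate, √(ICC × p × (1 - p)), around 6% is 2.4 points at ICC 0.01, 3.4 at 0.02 and 5.3 at 0.05. Around 11% it is 3.1, 4.4 and 7.0 points.

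**4. Secondary outcomes, same assumptions.** Placement-level t-test of time (normal data, 20,000 trials): 4.8 / 7.1 / 8.5 / 11.8 / 21.6% across the five ICCs. Analgesia at an assumed 80-90% success rate: about 5 / 7 / 8.7 / 12 / 21%. Fisher on complications at ICC 0.05: 3.5% at an assumed 1% rate, 7.4% at 2% and 10.3% at 3%. Number of attempts was not simulated.

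**5. A test that uses the weeks.** Pooled two-sample t-test on eight weekly failure proportions, 6 df. Its type I error is 4.3-5.4% at 6-11% rates. At 2-3% rates it is about 6% at ICC 0, falling to 2.6-3.6% at 0.05. Power for 11% against 1%:

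| ICC | 0 | 0.005 | 0.01 | 0.02 | 0.05 |
|---|---|---|---|---|---|
| 10% attrition | 77% | 73% | 69% | 61% | 45% |
| 20% attrition | 73% | 69% | 64% | 58% | 43% |

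A noncentral-t check at ICC 0.01 with all 30 analysed: weekly variance 0.0539 × 1.29 / 30 = 0.00232, standard error √(2 × 0.00232 / 4) = 0.0340, noncentrality 0.10 / 0.0340 = 2.94, power 69%. Simulation of the same case gives about 73%.

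The design effect alone, with no loss of degrees of freedom, gives 88 / 84% at ICC 0 and 79 / 75% at 0.01. The 6 df therefore cost about 88 - 77 = 84 - 73 = 11 points at ICC 0, before any clustering.

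**The case against.** The strongest reply is that the size of the problem is assumed. There is no ICC and no weekly data, and placements on one floor, shared evenly among grades of staff, may vary little by week. Errors near 20% need ICC 0.05, a weekly SD of 5 to 7 points, which that arrangement argues against. This stands as a limit on magnitude. It does not rescue the plan, which relies on ICC 0 without saying or justifying so; even sharing of placements does not exclude weekly differences in patients or individual operators.

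Fisher's test is conservative. That holds at 2-3% rates, where it is chosen in about 96% (2%) and 79% (3%) of trials at ICC 0.01. At the plan's own average of 6% it is chosen in only 11%, and at 11% never.

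The planned test still rejects often under 11% against 1%: 88 / 83% at ICC 0.01 and 86 / 81% at 0.02 after 10% / 20% attrition. Part of that reflects inflated error, so it cannot be read as power at 5%.

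The 0.004 threshold for 240 analysed depends on the plan's continuity-corrected 107; the uncorrected benchmark is more lenient, as shown above.

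The weekly t-test also has limits. At 2-3% rates with no weekly variation it rejects about 6%, more than the planned rule. Its quoted power needs the pooled variance: a Welch version gave 63 / 58% at ICC 0 after 10% / 20% attrition. These points affect how the remedy is specified, not whether one is needed. Use of the alternate kit within a week was not modelled; as an exception it does not change the randomised unit.

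**Conclusion.** The concern holds. The design randomises weeks, while the sample size and all planned tests assume independent placements, and nothing in the documents bridges the two. The 107 is not an arithmetic slip; its independence assumption does not match the allocation.

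The consequence is conditional. With no weekly variation there is no inflation. At ICC 0.005 to 0.02 and failure rates of 6-11%, the primary test's error is about 6.6% to 12% with all 240 analysed. At 2-3% rates it exceeds 5% clearly only near ICC 0.05. A weekly t-test that roughly holds its level at 6-11% rates has less than 80% power after the planned attrition even at ICC 0.

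These figures assume 4 + 4 weeks of equal size, beta-binomial weekly rates and analysis under the week's kit. Confidence is high in the mismatch; the magnitude depends on an ICC the documents do not give. It should be corrected before the analysis.

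**What to change.** 1. **Primary outcome.** State that week is the unit of randomisation and make the comparison week-aware, for example a pooled two-sample t-test on weekly first-attempt failure proportions with (weeks - 2) df. Analyse each placement under the kit assigned to its week, including those where the alternate kit was used. Acknowledge that the test's error is about 6% at 2-3% failure rates with no weekly variation.
2. **Secondary outcomes.** Compare time, number of attempts, needle manipulations and 30-minute analgesia on weekly summaries in the same way. Report the complication tests as descriptive, without claiming that Fisher's test protects against clustering.
3. **Sensitivity analysis.** Use a GEE or mixed model with a small-sample correction only in this role, and report it as not estimable if one kit has no failures. Under 11% against 1% and ICC 0-0.01 that occurs in 34-38% of trials at 10% attrition and 38-42% at 20%.
4. **Study Size.** State an assumed week ICC and the resulting power after the planned 10-20% attrition, using the power table above.

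The cost is protocol text; the study form already records date and kit, so week can be derived. No extra enrolment is required, but the stated power falls. If the sponsor wants 80% restored, more weeks are needed: 5, 6 and 7 per kit at ICC 0.01, 0.02 and 0.05 before attrition, against 4 planned. At 30 placements a week, one extra week per kit adds 60 placements.
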